4.4. Measure to minimize bias

Study participants eligible for treatment will be randomly assigned to one of the treatment arms using a computer-generated, stratified block randomization code. The random allocation sequence with varying random blocks of 4 and 8 (or 5 and 10, respectively) stratified by 2 levels of baseline infection intensity (light and moderate *T. trichiura* and hookworm infections) will be provided by a statistician. Study-site investigators will be aware

of the study group assignment, whereas participants and laboratory technicians will be blinded.

Placebo controlled trials reduce the risk of potential bias that can also interfere with the observed outcomes. In previous studies (e.g. Coulibaly et al. 2017 Lancet Global Health), we have observed moderate cure and egg reduction rates in placebo treated children likely due to the low sensitivity of anthelminthic diagnostics. Children treated with placebo will be treated at follow up (3-weeks post treatment) with 400 mg albendazole. This treatment delay does not cause any harm.

4.5. Study duration and duration of subject participation

The trial will last for a maximum of 6 months. The screening for the baseline will start four to six weeks prior to the treatment. Follow up screening will take place 14-21 days post-treatment and last for about three weeks. Schedules of visits are summarized below.

4.6. Schedule of visits

	Screening					Follow up
	-28 to -1		Hours			2-3 weeks
	days	0		1-8	24	
Informed consent	Х					
Diagnosis (stool examination)	×		ent			×
Demographics	X		Randomization and treatment			
Medical history		Х	and t			
Clinical examination		Х	ation			
Biochemical parameter		Х	domiz			X
PK sampling		Х	Rand	Х	X	
Capturing AEs				X (3h)	X	x
Capturing SAE				X (3h)	X	Х

5. Selection of the trial subjects

5.1. Recruitment

The study will be carried out in different age groups in areas endemic for *T. trichiura* and hookworm in Côte d'Ivoire. Age groups investigated include preschool-aged children 2-5 years old, school-aged children 6-12 years old and adults of 21 years or more.

The parents/guardians of the children and potential participating adults will be invited to participate in an informational meeting. Community members will be encouraged to ask questions in an open discussion forum. The parents/guardians will then be approached individually to explain and discuss the purpose and procedures of the study, including potential benefits and risks.

5.2. Inclusion criteria

- 1. Male and female preschool-aged children (2-5 years), school-aged children (6-12 years) and adults (≥21 years) infected with *T. trichiura*/hookworm.
- 2. Written informed consent signed by study participant/parent/guardian and written assent in the case of school-aged children.
- Positive for *T. trichiura*/hookworm by at least two slides of the quadruple Kato-Katz thick smears and infection intensities of at least 100 eggs per gram of stool (EPG).
- 4. Agree to comply with study procedures, including provision of two stool samples at the beginning (baseline) and approximately three weeks after treatment (follow-up).

5.3. Exclusion criteria

- 1. Presence of acute or uncontrolled systemic illnesses (e.g. severe anemia, infection, clinical malaria) as assessed by a medical doctor, upon initial clinical assessment and liver function tests.
- 2. Known or reported history of chronic illness such as HIV, acute or chronic hepatitis, cancer, diabetes, chronic heart disease or renal disease.
- 3. Prior treatment with anthelmintics (eg, diethylcarbamazine [DEC], suramin, ivermectin, mebendazole or albendazole) within 4 weeks before planned test article administration.
- Received any investigational drugs or investigational devices within 4 weeks before administration of test article that may confound safety and/or efficacy assessments.
- 5. Known or suspected allergy to benzimidazoles.
- 6. Pregnant (urine testing) or breastfeeding women.

Participants who were diagnosed with a STH infection, but who were excluded from the study due to one or several of the above-mentioned exclusion criteria, including withdrawals will be offered standard anthelminthic treatment (albendazole). Children suffering from

clinical malaria (fever plus positive diagnostic test) will be treated according to national guidelines but will not be included in the trial.

5.4. Criteria for discontinuation of trial

A subject can be discontinued from the study for the following reasons:

- 1. Withdraws from the study (this can happen anytime as participation is voluntary and there are no further obligations once a child withdraws).
- 2. At the discretion of the Principal Investigator, if the participant is not compliant to the requirements of the protocol or participation places the study subject at undue risk.

Discontinued subjects will not be replaced. If, for any reason, a subject is discontinued from the study before the end of treatment evaluations, the safety procedures planned (adverse events monitoring) will be conducted.

5.5. Treatment of subjects

400 mg chewable tablets of albendazole (Zentel®) will be obtained from Glaxo Smith Kline. Tablets will be split to obtain 200 mg and 600 mg dosages. Matching placebo tablets will be obtained from Fagron, Germany.

Participants will receive a small breakfast two hours prior to treatment and breakfast and lunch during the day once absorption of the drug is complete.

All drugs will be administered in the presence of the investigator(s), and ingestion confirmed. This will be recorded with the time and date of dosing. Subjects will be asked not to take any drugs other than those prescribed by the study medical team. After ingestion of the medication, the subjects will be observed for 3 hours to ensure retention of the drug. Vomiting within 1-hour post-dosing will require re-dosing. The subjects will not be allowed more than one repeated dose. No re-administration will be needed for subjects vomiting after one hour.

On each treatment day about 40 participants will be treated with the different dosages. In case any serious adverse events will be observed, the study will be put on hold until the data has been reviewed and a decision taken within the entire study team whether the study can be continued or has to be stopped. On the treatment day, participants presenting a serious medical situation as judged by the physician of the project will be kept at the hospital level under close supervision by the medical team, after the parents (for children) have been informed on the reasons for the prolonged hospitalization. Also, in order not to break the surveillance of the undesirable effects of those whom we will allow to go back home at the end of the treatment day, security measures will be taken: (i) a card containing at least three phone numbers of the investigators and the study physician will be given to the parents

(children) or the participant himself (adults). This card including the phone numbers on it will remain valid through the duration of the clinical trial; (ii) for the 24-hour period following treatment, a telephone unit transfer of at least 2000 CFA will be transferred to each participant or the participant's parent so that they can call the investigators at any time; (iii) a medical team with an emergency kit will stay within the community for 24 hours following the treatment; and (iv) on the basis of an agreement to be signed with the responsible health district, an ambulance will be made available to enable rapid evacuation if necessary. All the financial implications of these arrangements will be fully supported by the project.

The Principal Investigator is responsible for drug accountability at the study site. Maintaining drug accountability includes careful and systematic study drug storage, handling, dispensing and documentation of administration.

We will be working with children or adults in rural areas. Participants who are involved in agricultural activities and migrating between locations will be difficult to follow by the investigators. We will provide them with phone numbers and follow them up with the help of health workers in case adverse events occur.

5.6. Concomitant therapy

All medications taken one month before and during the study period must until the last stool examination between day 14 and 21 (follow-up) be recorded with indication, dose regimen, date and time of administration.

Medication(s)/treatment(s) permitted during the trial

 Analgesics and antipyretics are allowed to be given to the subjects in case of fever, antiemetics to prevent nausea and vomiting and/or antibiotics to prevent or treat bacterial superinfection.

Medication(s)/treatment(s) NOT permitted during the trial

 No other active drugs or use of grapefruit juice against helminths are permitted during the trial

6. Assessment of safety

Few adverse events have been reported following albendazole administration in STH-infected individuals. The most common adverse events were abdominal cramps, headache, nausea, diarrhea, fever and vertigo [10]. The safety profile of albendazole will be assessed through the recording, reporting and analysis of baseline medical conditions, adverse events and a physical and clinical examination as described in section 4.3.1.

6.1. Adverse event definitions

The term "adverse event" could include any of the following events which develop or increase in severity during the course of the study, after administration of the study product:

- a) Any unfavourable and unintended signs, symptoms or disease temporally associated with the use of a medicinal product, whether or not considered related to the condition under study and the study product;
- b) Any abnormality detected during physical and clinical examination and whole blood analysis.

The medical conditions present at the initial trial visit that do not worsen in severity or frequency during the trial will not be defined as adverse events but be considered baseline medical conditions.

The observation time for adverse events starts when the treatment is initiated until the last follow-up examination (21 days after drug administration).

These data will be recorded on the appropriate CRF sections, regardless of whether they are thought to be associated with the study or the drug under investigation. Associated with the use of the drug means that there is a reasonable possibility that the event may have been caused by the drug (see also relatedness definitions below).

6.1.1. Severity grading

Adverse signs or symptoms will be graded by the Investigator as mild, moderate, severe or life threatening according to the following definitions (https://evs.nci.nih.gov/ftp1/CTCAE/CTCAE 4.03 2010-06-14 QuickReference 5x7.pdf):

Grade	Definition
1	Mild: the subject is aware of the event or symptom, but the event or symptom is
	easily tolerated.
2	Moderate: the subject experiences sufficient discomfort to interfere with or
	reduce his or her usual level of activity.
3	Severe: significant impairment of functioning: the subject is unable to carry out
	his or her usual activities.

- 4 Life threatening or disabling
- 5 Death related to adverse events

6.1.2. Relatedness

Relatedness will be assessed as defined below based on the temporal relationship between the adverse event and the treatment, known side effects of treatment, medical history, concomitant medication, course of the underlying disease and trial procedures.

Possibly related: an adverse event which can medically (pharmacologically/clinically) be attributed to the study treatment.

Unrelated: an adverse event which is not reasonably related to the study treatment. A reasonable alternative explanation must be available.

6.1.3. Expectedness

Expected adverse event: Any adverse event of albendazole reported in the literature or on the drug package leaflet and listed in the consent form. These adverse events are detailed in the drug package leaflet (Appendix 1).

Unexpected adverse event: Any adverse event, the nature, frequency, specificity or severity of which is unanticipated and not consistent with the available risk information described for these drugs.

6.1.4. Serious adverse events

According to the ICH "Clinical Safety Data Management: Definitions and standards for expedited Reporting E2A" (http://www.ich.org/fileadmin/Public_Web_Site/ICH_Products/Guidelines/Efficacy/E2A/Step4/E2A Guideline.pdf), a serious adverse event (SAE) includes any event that:

- 1. results in death:
- 2. is life threatening, meaning, the subject was, in the view of the Investigator, at immediate risk of death from the reaction as it occurred, *i.e.*, it does not include a reaction that, had it occurred in a more serious form, might have caused death;
- 3. results in persistent or significant disability/incapacity, *i.e.*, the event causes a substantial disruption of a person's ability to conduct normal life functions;
- 4. requires, in-patient hospitalization or prolongation of existing hospitalization;

- 5. creates a congenital anomaly or birth defect (not relevant for this study);
- 6. is an important medical event, based upon appropriate medical judgment, that may jeopardize the patient or subject or may require medical or surgical intervention to prevent one of the other outcomes defining serious.

A "severe" adverse event does not necessarily meet the criteria for a "serious" adverse event. Serious adverse events are reported from consent to the last follow-up examination (14-21 days post-treatment).

Serious adverse events that are still ongoing at the end of the study period will be followed up to determine the final outcome.

The causality of any serious adverse event that occurs after the study period and its possible relatedness to the study treatment or study participation will also be assessed by the investigators as described in section 6.1.2.

6.1.5. Suspected unexpected serious adverse reactions

A suspected unexpected serious adverse reaction (SUSAR) is an unexpected adverse reaction which also meets the definition of serious adverse events.

6.2. Methods of recording and assessing adverse events

Subjects will be kept for observation for at least 3 hours following treatment for any acute adverse events. If there is any abnormal finding, the local study physician will perform a full clinical and physical examination and findings will be recorded. An emergency kit will be available on site to treat any medical conditions that warrant urgent medical intervention. Adults, school-aged children and the mother of preschool-aged children will also be interviewed 3 and 24 hours after treatment and at follow-up (2-3 weeks after treatment) about the occurrence of adverse events (see chapter 4.6).

Information on all adverse events (onset, duration, intensity, seriousness and causality) will be immediately entered in the appropriate adverse event module of the case report form (CRF) that serves as source document. For all adverse events, sufficient information will be pursued and/or obtained so as to permit i) an adequate determination of the seriousness of the event (i.e. whether the event should be classified as a serious adverse event); ii) an assessment of the casual relationship between the adverse event and the study treatments and iii) an assessment of intensity of adverse events will be judged by the study physician.

All serious adverse events or SUSARs must be reported as described in Section 6.3.

6.4. Safety reporting to Health Authorities and Ethics Committees

The sponsor-investigator will send appropriate safety notifications to Health Authorities in accordance with applicable laws and regulations. Additionally, this information will be provided to 'Ethikkomission Nordwest- und Zentralschweiz' (EKNZ, Switzerland) and the ethics committee and the 'Direction de la Pharmacie, du Médicament et des Laboratoires (DPML)' in Côte d'Ivoire according to national rules. Fatal or life-threatening serious adverse events or SUSARs will be reported within 24 hours after the event followed by a complete report within 7 additional calendar days. The sponsor will suspend dosing of further participants (until review by the PI and study physician(s)), if there is sufficient cause as determined by the investigators including the study physician, which attests that the continuity of the study will jeopardize the health or safety of participants. The study will be suspended pending a new positive decision by the two accredited local aforementioned institutions. The investigator will take care to inform all participants. Participants already enrolled in the study will complete the trial. Other serious adverse events and SUSARs that are not fatal or life-threatening will be filed as soon as possible but no later than 14 days after first knowledge by the sponsor.

7. Statistics

7.1. Definition of primary endpoint

Cure rate is the primary outcome of our study. Since these might be influenced by infection intensity, treatment allocation will be stratified by baseline infection intensity.

7.2. Justification of number of trial subject

Since the existence of a drug effect is well known, the main aim of the study is the elucidation of the nature of the dose–response relationship. A series of simulations was carried out to determine the required sample size. We assumed a true cure rate against hookworm of 5%, 30%, 50%, 70% and 80% (for 0, 200, 400, 600 and 800 mg) and of 5%, 10%, 20%, 30% and 40% against *T. trichiura* and loss to follow up of 5%. We estimated that enrolling 40 participants per arm will be sufficient to predict the dose response curve with a precision (defined as median distance between prediction and confidence band) of about 10 percentage points. The suggested sample size is also in line with the recommendations from Klingenberg et al. 2009 [11]. This sample size is sufficiently high to determine the key PK parameters as well as PK/PD relationships.

7.3. Description of statistical methods

The primary analysis will use the full analysis set (available case population) according to the intention to treat principle defined as all randomized subjects which provide any follow-up data. Only subjects which were negative at baseline and erroneously randomized will be excluded from the analysis. In addition, a per-protocol analysis will be conducted. CRs will be calculated as the percentage of egg-positive participants at baseline who become egg-negative after treatment. EPG will be assessed by adding up the egg counts from the quadruplicate Kato-Katz thick smears and multiplying this number by a factor of six. The ERR will be calculated (ERR = (1-(mean at follow-up/mean at baseline))*100).

Geometric mean egg counts will be calculated for the different treatment arms before and after treatment to assess the corresponding ERRs. Bootstrap resampling method with 5,000 replicates will be used to calculate 95% confidence intervals (CIs) for ERRs point estimates. E_{max} models using the DoseFinding package of the statistical software environment R will be implemented to predict the dose-response curves in terms of CRs and ERRs.

On the basis of the LC-MS/MS measurements, the following PK parameters for plasma will be calculated:

C_{max} maximal plasma concentration

t_{max} time to reach C_{max}

AUC area under the curve, from 0 to 24h and 0 to inf

T_{1/2} elimination half-life

 C_{max} and T_{max} will be observed values derived from the plasma concentration time profile. AUC and $T_{1/2}$ will calculated with the software WinNonlin (Version 5.2, Pharsight Corporation, USA) using noncompartmental analysis. The elimination half-life will be estimated by the equation: $T_{1/2} = ln2/\lambda$, where λ will be determined by performing a regression of the natural logarithm of the concentration values during the elimination period.

Further PK analysis will be undertaken fitting a structural compartmental PK model with the software NONMEM 7 via nonlinear mixed effects modeling (allowing for both between patient variation and random effects). This model will describe the blood drug levels in time, allowing one to investigate variation between patients in drug levels. In addition, pharmacometric-pharmacodynamic (PKPD) analysis will be undertaken via NONMEM to investigate the drivers of cure and/or burden reduction and potentially any covariates with drug levels.

Adverse events will be evaluated descriptively as the difference of proportion reporting adverse events before and after treatment.

If possible, a sensitivity analysis will be conducted where double infections enrolled in one trial will be included in the other trial.

8. Data management and data quality control

The investigators are responsible for an adequate data quality. Prior to the initiation of the study, a short investigators meeting will be held with the investigators and their study coordinators and a member of the Swiss TPH. This meeting will include a detailed discussion of the protocol, performance of study procedures, CRF completion, specimen collection and diagnostic methods.

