standardized questionnaire (for preschool-aged children this will be administered to the caregiver of the child). In addition a clinical examination will be performed by the study physician and venipuncture to examine biochemical parameters in the blood will be carried out by study nurses before treatment. Adults, children and caregivers of preschool-aged children will also be interviewed before treatment, 3 and 24 hours after treatment, and at follow-up (2-3 weeks after treatment) about the occurrence of adverse events. The efficacy of the treatment will be determined 14-21 days post-treatment by collecting another two stool samples. All stool samples will be examined with duplicate Kato-Katz thick smears. A subsample of children and adults will be sampled using finger pricking for micro-blood sampling at 0, 1, 2, 3, 4, 6, 8, 24 hours post-dosing to evaluate pharmacokinetic parameters. **Statistical Analyses** An available case analysis (full analysis set according to the intention to treat principle) will be performed, including all subjects with primary endpoint data. Supplementary, a per-protocol analysis will be conducted. CRs will be calculated as the percentage of egg-positive subjects at baseline who become eggnegative after treatment. Geometric mean egg counts will be calculated for the different treatment arms before and after treatment to assess the corresponding ERRs Bootstrap resampling method with 5,000 replicates will be used to calculate 95% confidence intervals (CIs) for ERRs. E_{max} models using the DoseFinding package of the statistical software environment R will be implemented to predict the dose-response curves in terms of CRs and ERRs. Noncompartmental and nonlinear mixed-effects (NLME) modeling will be used to determine PK parameters. **GCP** statement This study will be conducted in compliance with the protocol, the current version of the Declaration of Helsinki, ICH-GCP E6 (R2) guidelines as well as all national legal and regulatory requirements. **Key explanation for the** This study will be carried out in children, since an infection with T. inclusion of children trichiura and hookworm occurs most often in children and they are the main targets of preventive chemotherapy programs. Moreover, the exact dosage of albendazole in preschool and school-aged children has not yet been determined. Recruitment procedure Participants will be recruited from rural communities situated in Côte d'Ivoire and identified to have at least a moderate infection risk (prevalence: 10-49%) of *T. trichiura* or hookworm.

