4.3. Trial design

4.3.1. Baseline survey

Stool samples collection

Two stool samples will be collected from each participant until a total of 560 hookworm-infected participants (160 preschool-aged children, 200 school-aged children and 200 adults) and 480 *T. trichiura* infected participants (160 preschool-aged children, 160 school-aged children and 160 adults) are identified.

[figure not shown]
The Kato-Katz technique will be used for the quantitative assessment of STH infections. Two stool samples will be collected from each participant before treatment and from each sample duplicate Kato-Katz thick smears (41.7 mg each) will be prepared [8]. The slides will be analyzed under a microscope by experienced technicians and a subsequent independent quality control of sample results (approximately 10%) will be conducted. Results are considered correct if the following tolerance margin is not exceeded: (i) No difference in presence/absence of hookworm, A. lumbricoides and T. trichiura, (ii) egg counts are +/-10 eggs for counts ≤100 eggs or +/-20% for counts >100 eggs (for each species separately) [9]. In case discrepancies above the tolerance margin are noted in one or more slides, all slides are re-read by the local technicians. The new results are discussed, so that in case of discordant results, slides can be re-evaluated to reach consensus. Infection intensity expressed as the arithmetic and geometric mean egg counts per gram of stool (EPG) will be calculated for each treatment arm. All microscopically analyzed quadruplicate Kato-Katz thick smears will be destroyed within one day (after passing the quality control). Since drug efficacy could be influenced by genetic aspects, ~2 g of stool sample from each participant will be preserved in ethanol for further genetic analyses of hookworm and T. trichiura in Côte d'Ivoire and Switzerland.

[figure not shown]
Clinical examination and biological exams

At baseline, the medical history of *T. trichiura* and hookworm-infected participants in the study will be assessed with a clinical and physical examination carried out by the study clinician, who will assess weight, height, body temperature, pulse rate and blood pressure. Rapid diagnostic tests for malaria will be done to assess the presence of a *Plasmodium* spp. co-infection. Hemoglobin (Hb) levels will be detected using HemoCue to exclude severely anemic participants (below 80 g/l and 70 g/l Hb in school-aged and preschool-aged children,

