8.1. Data collection

The data produced from this research project will fall into the following categories:

- Eggs counts of hookworm, Ascaris lumbricoides and Trichuris trichiura found in participants' stool samples using the Kato-Katz technique before (baseline) and after (follow-up) treatment.
- 2. Personal information such as name, age and gender of trial participants.
- Anthropometric and clinical characteristics of the trial participants collected using the study's case report form (CRF) such as weight, height, blood pressure, temperature hemoglobin levels, any abnormal medical condition or chronic disease.
- 4. Number and type of adverse events registered in the CRF and actively probed for 3and 24,hours after treatment. The same data will be collected during the collection of the first sample at follow-up.
- 5. Pharmacokinetic parameters such as Cmax, AUC or tmax analyzed from dry blood spots or Mitra® at 0, 1, 2, 3, 4, 6, 8, 24 hours post-dosing.

Data from categories 1-4 will be paper-captured and subsequently doubled entered (data entry SOP) into ACCESS data entry masks by two independent people for quality assurance. Both databases will then be cross-checked using the Data Compare utility of Epilnfo; any discrepancies will be corrected by consulting the hard copy. Data entered into ACCESS databases will only be accessible to authorized personnel directly involved with the study by use of a password. Data in category 1 will be saved both in .mdb, .xlsx and .csv. Data in category 2, 3 and 4 will be double-entered using an Epilnfo mask and saved in .mdb, .xlsx and .csv. All categories will be merged into a single master filed saved in .xlsx and .csv. Data will then be analysed as described in section 7. PK parameters derived from analyzing microblood samples will be merged and saved as a .xlsx file. Hard copies of the data such as parasitological sheets and CRFs will remain at IHI. Digital copies along with the databases will be transferred to the Swiss TPH after a Material Transfer Agreement has been signed by both the Swiss TPH and CSRS. All data is expected to not exceed 5GB.

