10.3. Subject information and consent

All parents or caregivers of eligible children and all adult participants (≥21 years) will be asked to sign a written informed consent sheet. Caregivers must have attained their majority (21 years in Côte d'Ivoire). In case the person is illiterate, an impartial witness that can read and write has to sign the consent and the illiterate participant to give a thumb print. Parents or caregivers will have sufficient time for reflection of their child's participation. Additionally, school-aged children (6-12 years) will be briefed verbally and written assent sought in form of their name written down or, if illiterate, by providing a thumb print. Community meetings will be conducted to explain the purpose and procedures of the study. The parents attending this meeting will receive a small provision to cover their costs for transportation to the study site (~US\$ 2). Information sheets are printed in French but will additionally be verbally translated into local languages (i.e. Abbé, Attié, Dioula, Moré) during community meetings. Participation is voluntary and participants have the right to withdraw from the study at any given point in time with no further obligations. Participation itself will not be awarded with compensation. Data collected until date of potential withdrawal will be analyzed and once analysis performed fully anonymized.

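### Does the times-six EPG rule inflate the egg reduction rate when a participant gives only one follow-up stool?

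*Combined protocol and SAP*

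**What the plan says.** Section 7.3 obtains EPG by "adding up the egg counts from the quadruplicate Kato-Katz thick smears and multiplying this number by a factor of six", and section 4.3.2 gives the same rule. Section 4.3.1 supplies the inputs: two stools are collected, and "from each sample duplicate Kato-Katz thick smears (41.7 mg each) will be prepared". Section 4.3.2 plans another two stools at 14–21 days.

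The full analysis set in section 7.3 is "defined as all randomized subjects which provide any follow-up data", less anyone negative at baseline and randomized in error. The Synopsis (Statistical Analyses) describes the same set as "including all subjects with primary endpoint data". Neither text states a minimum number of stools or smears.

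ERR is a secondary endpoint, defined in section 7.3 as one minus the ratio of the follow-up mean to the baseline mean. Section 7.3 names geometric means; section 4.3.2 names geometric and arithmetic. The primary endpoint, cure rate, depends only on whether any eggs are found.

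**The concern.** The multiplier fits one sampling pattern, while the analysis set admits others. A participant who gives one follow-up stool has two smears and belongs in the set, but has no EPG defined by the plan. If an analyst applied six regardless, that follow-up EPG would be half its proper value. Entry refers to quadruple smears (section 5.2), so the baseline value would usually be on the full scale and the error would not cancel in the ratio. ERR would then rise because of incomplete sampling rather than drug effect, and most where ERR is low. The bootstrap intervals would resample the same mis-scaled values and could not reveal it.

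Several sentences seem to make one-stool participants likely. Section 8.1 says "The same data will be collected during the collection of the first sample at follow-up". Section 5.5 says "Participants who are involved in agricultural activities and migrating between locations will be difficult to follow by the investigators". Section 10.3 says "Data collected until date of potential withdrawal will be analyzed".

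**Working it through.** **1. Reproduce the stated factor.** Factor = 1000 mg / (number of smears × 41.7 mg).

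- Four smears: 1000/166.8 = 5.995, that is 6, as stated.
- Three smears: 1000/125.1 = 7.99, that is 8.
- Two smears: 1000/83.4 = 11.99, that is 12.

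All three equal 24 × the mean count per smear read. Using 6 in place of 12 halves the EPG of that participant, not of the arm.

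**2. Number affected.** Section 7.2 assumes 40 per arm and 5% loss, so 40 × 0.95 = 38 are evaluable. The one-stool share *f* is not in the documents. Assume 5% or 10%: 38 × 0.05 = 1.9 and 38 × 0.10 = 3.8, about 2 or 4 people per arm.

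**3. Arithmetic-mean ERR if six is misapplied at follow-up only.** For true ERR *e*, reported ERR = 1 − (1 − *e*)(1 − *f*/2).

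| True ERR | *f* = 5% | *f* = 10% |
|---|---|---|
| 20% | 22.0% (+2.0) | 24.0% (+4.0) |
| 50% | 51.25% (+1.25) | 52.5% (+2.5) |
| 90% | 90.25% (+0.25) | 90.5% (+0.5) |

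With the same *f* in every arm, reported ERR = *f*/2 + (1 − *f*/2) × ERR. An Emax curve fitted to it has Emax reduced by 2.5% or 5% of its value, a raised intercept and an unchanged ED50. For geometric means this holds only approximately.

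**4. Geometric-mean ERR.** Zeros are unaffected by any factor, so the effect shrinks as the cured share *p* grows. High ERR also goes with high *p*: entry requires at least 100 EPG, so under a log(EPG + 1) convention ERR is at least 1 − 101^(−*p*) unless uncured counts rise. That floor is 60.3% at *p* = 20%, 75.0% at 30% and 90.05% at 50%. Large upward shifts are therefore confined to arms with few cures.

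A simulation shows the size. It used 400,000 draws per setting, lognormal baseline with median 300 EPG raised to at least 100, Poisson counts and gamma day-to-day variation. All distributions are assumed. Cured shares follow section 7.2; the residual count in the uncured is assumed.

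| Arm (cured; residual in uncured) | Geometric, *f* = 5% / 10% | Arithmetic, *f* = 5% / 10% |
|---|---|---|
| Placebo (5%; 80%) | +1.67 / +3.24 | +1.90 / +3.79 |
| *T. trichiura* 400 mg (20%; 50%) | +0.41 / +0.82 | +0.98 / +2.02 |
| Hookworm 400 mg (50%; 30%) | +0.04 / +0.09 | +0.38 / +0.75 |

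These are points of ERR, times-six minus times-twelve. Correct scaling does not restore four-smear precision: in the placebo arm the geometric ERR is 46.9% with four smears for everyone, and 47.4% or 47.9% with correct scaling at *f* = 5% or 10%.

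**5. Direction.** Section 5.2 requires at least two positive slides of the quadruple smear; it does not expressly require all four to have been read. If a share *g* had one baseline stool and six were used, arithmetic ERR would be 1 − (1 − *e*)/(1 − *g*/2). At *e* = 50% this is 1 − 0.5/0.975 = 48.7% for *g* = 5% and 1 − 0.5/0.95 = 47.4% for *g* = 10%. With equal shares at both visits the arithmetic error cancels.

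**6. The sentences on incomplete follow-up, read in place.** The one in section 8.1 times the adverse-event questions. The one in section 5.5 leads into phone contact and health-worker follow-up for adverse events. The one in section 10.3 concerns data kept after withdrawal. The 5% in section 7.2 is loss to follow-up. One-stool participants are plausible, but no passage gives or implies their number.

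**The case for a change.** The strongest case for a change is that the plan leaves the analyst a choice. One could use six as written, use twelve, or drop one-stool participants from ERR while keeping them for cure rate. These give different ERRs, and an analysis plan should settle such choices before results are seen. The remedy would be one sentence, and complete cases would be unaffected.

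The missing rule is real, and a sentence defining EPG as 24 times the mean count per smear read would do no harm. But the three options are not on an equal footing. The text attaches six to quadruplicate smears, so applying it to two goes beyond the wording and yields a quantity that is not eggs per gram. The smear mass is in section 4.3.1, and twelve follows from it at once. Dropping about 2 to 4 of 38 people from a secondary summary would cost little precision, and would not bias ERR if giving one stool is unrelated to outcome. Nor is the choice irreversible: section 8.1 has egg counts captured and double-entered, so EPG can be recomputed at any time.

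**Conclusion.** The concern does not call for a change. The factor of six is correct for the sampling the plan prescribes, and the plan nowhere tells anyone to use it for two smears. What remains is an unspecified case that a competent analyst fills by scaling to the smears read.

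Even if it were filled wrongly, the geometric-mean ERR named in section 7.3 would move by under 0.1 point in the hookworm 400 mg arm and by about 3 points in placebo. The arithmetic-mean ERR would move by up to about 4 points at a true ERR of 20%. These sizes rest on an assumed 5–10% one-stool share at follow-up, four smears at baseline and assumed egg-count distributions. A one-stool baseline would reverse the direction. The documents give no reason to expect the share to differ by dose. The primary cure rate and its dose-response curve do not use the factor.
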